The study will comprise a randomized, double-blind parallel-arm controlled clinical trial to ascertain whether combination nicotine patch + lorcaserin will be more effective than nicotine patch alone as a treatment for reduction of ad libitum smoking behavior and time-to-lapse in a simulated quit-smoking situation during the first 2 weeks. After the first 2 weeks, all participants will receive the same combination treatment for the remainder of the study. The study will include N=60 randomized participants. This study will include a screening visit, a baseline visit, a laboratory visit, a visit one day prior to the Target Quit Date (TQD), 4 post quit visits, and a 6 month follow up visit (for eligible participants). Participants will be randomized to receive nicotine patch + lorcaserin or nicotine patch + placebo for the first 2 weeks. The nicotine patch will be administered according to the standard dosing regimen of 21mg daily. Lorcaserin will be administered at a dose of 10 mg twice a day, a dose used in weight loss treatment. Ad libitum smoking will be assessed weekly using daily diary recordings of cigarettes smoked per day as well as the objective index of expired air carbon monoxide (CO) levels measured at the study visits. After 2 weeks, a laboratory session will be conducted in which withdrawal symptoms will be assessed as well as the ability to delay smoking in a simulated smoking lapse paradigm validated by McKee et al. (2012). In this paradigm smokers are allowed to smoke but are offered a monetary incentive to delay smoking; the amount of this incentive decreases over time during the session. The outcome measure is the time-to-lapse, which has been shown to increase following smoking cessation medications such as varenicline and bupropion, and decrease following manipulations which are known to trigger relapse, e.g., stress, alcohol consumption. Following the laboratory session, the group that receives nicotine patch + placebo will be switched to receiving nicotine patch + lorcaserin and the nicotine patch+ lorcaserin group will continue receiving nicotine patch+ lorcaserin, for an additional 2 weeks leading up to a scheduled target quit-smoking date (TQD). Treatment with nicotine patch + lorcaserin will continue for an additional 10 weeks after the TQD for all participants, followed by

[figure not shown]
two weeks during which the dosage of the nicotine patches will be tapered (one week of 14mg patches and one week of 7mg patches).

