The treatment groups are as follows:

Group A: 21mg nicotine patch + lorcaserin 10mg twice daily for the 14 week study period followed by a 2 week taper of the nicotine patch (14mg for 1 week; 7mg for 1 week).

Group B: 21mg nicotine patch + placebo for the first 2 weeks; 21mg nicotine patch + lorcaserin 10mg twice daily for the next 12 weeks followed by a 2 week taper of the nicotine patch (14mg for 1 week; 7mg for 1 week).

The Study timeline is shown below:

Blinding

In order to maintain a double-blind assignment to treatment conditions, subjects receiving nicotine patch alone (Group B) will receive placebo lorcaserin tablets during the first two weeks.

Screening and Session Procedures

Interested potential subjects will respond to advertisements by contacting our Center to be phone screened. Potential subjects will be given a brief description of the study and will be asked questions to assess eligibility and interest. Eligible subjects interested in participating will be scheduled for the medical history and physical examination screening visit.

After granting their informed consent, potential subjects will be given the HIPAA Notice of Privacy Practices. They will also complete a medical history form and will have their blood pressure, pulse, weight, height, temperature and expired air CO measured.

Subjects will provide smoking history information, a saliva sample, blood (maximum of 20mL) for tests to measure general health, and urine for urinalysis and illicit drug testing. Women of child bearing potential will also have a serum pregnancy test. The study physician or one of his assistants will perform a physical examination and an ECG. The

initial target Quit Day for all the subjects will be established at screening. The screening visit will last approximately 2 hours.

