Blood and urine specimens will be sent to LabCorp for processing. The results of laboratory blood and urine tests will not routinely be given to participants to send or be sent to their physician to include in their medical record. However, if the subject's lab results are outside the acceptable range for participation in the study the Physician/P.A. will send the subject a medical exclusion letter and a copy of the lab results. Participants who are accepted into the study but need medical follow up due to minor abnormalities in lab results will also be informed by letter from the Physician/P.A. A copy of the laboratory results will be included with the letter, which will also indicate that the condition does not interfere with his/her participation in the study.

The time commitment for subjects is 16 weeks: 4 weeks of pre-cessation treatment before the scheduled Quit Day and 12 weeks of additional post-Quit Day treatment, plus one follow-up session at six months (if eligible) after the Quit Day.

Questionnaires will be completed within REDCap on a desktop computer in the Center office. The technician will log on to the REDCap site and will open the questionnaires for the subjects. Subjects will only have access to their questionnaires. Access to any other websites will be blocked by Psychiatry Information Technology.

Session P1

The first study visit will take place approximately one week after the screening visit. Subjects will complete baseline questionnaires and will be randomized to either Group A (nicotine patch + lorcaserin) or Group B (nicotine patch + placebo). Subjects will be tested for exhaled air carbon monoxide and smoking related chemicals in the saliva. They will also have their blood pressure, heart rate and weight measured. Females of child bearing potential will also complete a urine pregnancy test which must be negative in order to continue study participation. Subjects will also complete questionnaires rating craving, withdrawal symptoms, side effects, and sensory experience.

Subjects will be given a supply of study medications (depending on randomization) to use for 2 weeks and will receive verbal and written instructions on how to take them.

Subjects will also be given diaries to record medication use and the number of cigarettes smoked each day and will be instructed to return the diaries at the next visit. They will also be asked to return any unused medications for proper disposal and compliance monitoring.

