Subjects will be called within three days after the first day of treatment to make sure that medications are being used as directed.

Session P2

The second study visit will take place 2 weeks after the first visit. Subjects will be tested for exhaled air carbon monoxide and smoking related chemicals in the saliva. Subjects

will also have their blood pressure, heart rate and weight measured. In addition, they will also complete questionnaires rating craving, withdrawal symptoms, side effects, and sensory experience.

A laboratory session will be conducted at this visit. Participants will be asked to refrain from smoking after midnight the night before the session. After an additional 2 hour period in which subjects refrain from smoking, withdrawal symptoms will be assessed as well the ability to delay smoking in a simulated smoking lapse paradigm validated by McKee et al (2012). In this paradigm smokers are allowed to smoke but are offered a monetary incentive to delay smoking, which decreases over time in the session.

Subjects in both Group A and Group B will be given a supply of study medications (nicotine patch + lorcaserin). Following the P2 laboratory session, the group that received nicotine patch + placebo will be switched to receiving nicotine patch+ lorcaserin, and the nicotine patch+ lorcaserin group will continue receiving nicotine patch+ lorcaserin, for an additional 2 weeks leading up to a scheduled target quit-smoking date (TQD).

Subjects will also be given diaries to record medication use and the number of cigarettes smoked each day and will be instructed to return the diaries at the next visit. They will also be asked to return any unused medications for proper disposal and compliance monitoring.

Session P3 (the day before Quit Day)

The third study visit will take place 2 weeks after the second visit (and one day prior to the Quit Day). Subjects will be tested for exhaled air carbon monoxide and smoking related chemicals in the saliva. Subjects will also have their blood pressure, heart rate and weight measured. Females of child bearing potential will also complete a urine pregnancy test which must be negative in order to continue study participation. They will also complete questionnaires rating craving, withdrawal symptoms, side effects, and sensory experience.

Subjects will be dispensed a sufficient supply of nicotine patches and lorcaserin to last until the next scheduled visit.

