DATA ANALYSIS & STATISTICAL CONSIDERATIONS

The primary outcome measure will be the time-to-lapse during the laboratory session. McKee et al. (2012) reported an effect size of ~0.8 on this measure, and obtained significant results assessing the therapeutic effects of bupropion and varenicline with n=20 per group. With n=30 per group in the proposed study, and using a one-tailed alpha=0.05 (the hypothesis is one-tailed inasmuch as there would be no interest in pursuing the development of lorcaserin unless an increase in time-to-lapse is demonstrated), we should obtain over 90% power to detect a comparable effect. Secondary outcomes that will be compared between groups include the percent reduction in ad libitum smoking during the first 2 weeks, and withdrawal symptoms reported after 2 hours of smoking abstinence in the laboratory, measures that have been sensitive to treatment in our previous studies of nicotine replacement therapy (NRT) and other treatments. The two treatment groups will be compared on these measures using ANOVA-based statistical methods.

Continuous abstinence from smoking during weeks 7-10 after the quit date will also be tabulated, and 90% confidence intervals will be calculated. Abstinence will also be correlated with the reduction in ad libitum smoking in the first 2 weeks to determine whether smoking reduction may be a useful early marker of therapeutic efficacy. Among smoking-abstinent participants, weight gain relative to baseline will also be assessed, and 90% confidence intervals will be calculated.

Tolerability of treatment will be assessed by tabulating side effect frequencies and degree of adherence to taking medications (percent of total doses taken, assessed by self-report diaries and counts of returned medications at each session).

DATA & SAFETY MONITORING

Description of BP monitoring procedures after study enrollment

After study enrollment, if blood pressure during return sessions is above 160/100, then the following actions will be taken to enhance subject safety:

- If BP >210/100 with symptoms of malignant hypertension: stop experiment interventions and refer to appropriate medical treatment. Resume participation and continue to be monitored if BP is no greater than 140/100.

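### Laboratory withdrawal at P2 is compared with no baseline covariate named, although withdrawal is already rated at P1 before study drug is used; pre-specifying ANCOVA on the P1 score would be a near-free improvement to a secondary outcome

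*Combined protocol and SAP*

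**What the plan says.** The Data Analysis & Statistical Considerations section makes time-to-lapse the primary outcome. Among the secondary outcomes compared between groups it lists "withdrawal symptoms reported after 2 hours of smoking abstinence in the laboratory". The method is given in one sentence: "The two treatment groups will be compared on these measures using ANOVA-based statistical methods". No covariate, model term or baseline adjustment is named there or elsewhere in the document.

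Under Session P1, the visit at which participants are randomised, the protocol states: "Subjects will also complete questionnaires rating craving, withdrawal symptoms, side effects, and sensory experience". The same section says "Subjects will be given a supply of study medications (depending on randomization) to use for 2 weeks", so study drug is used only after that visit.

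Under Session P2, the laboratory rating is described as follows: "After an additional 2 hour period in which subjects refrain from smoking, withdrawal symptoms will be assessed". Before that, "Participants will be asked to refrain from smoking after midnight the night before the session". No comparable abstinence request is written for P1.

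**The concern.** Withdrawal is part of the trial's first aim, and the results are meant to support a later grant application, so precision on this outcome is useful. With about 30 participants per group, a comparison that ignores a pre-treatment measure of the same symptoms may discard information the trial has already collected.

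The method wording also leaves the model open. It could mean unadjusted ANOVA, ANCOVA, an analysis of change or a repeated-measures model. These can give different p-values on the same data and do not have the same power, so the choice is better fixed in advance.

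**Working it through.** **Inputs from the plan.** 30 per group; one-tailed alpha of 0.05, effect size about 0.8 and power over 90%, all stated for time-to-lapse only.

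**Inputs assumed.** The documents give no effect size, standard deviation, P1–P2 correlation, sidedness or dropout for withdrawal. I take d=0.5 as illustrative, r from 0 to 0.5, both one-sided and two-sided 5% tests, and no dropout.

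**Step 1: the plan's own figure.** The noncentrality is d × √(n/2) = 0.8 × √15 = 3.098. With 58 degrees of freedom the one-sided critical value is 1.672, and the noncentral t gives power of 92.2%. The stated figure of over 90% reproduces.

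**Step 2: withdrawal without a covariate.** The noncentrality is 0.5 × √15 = 1.936 on 58 degrees of freedom. Power is 60.6% one-sided and 47.8% two-sided.

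**Step 3: withdrawal with the P1 score as covariate.** ANCOVA multiplies the variance of the treatment difference by (1 − r²). Chance baseline imbalance multiplies it by 1 + 1/(N − 4) = 1 + 1/56 = 1.018, with N=60. The combined factor is V = (1 − r²) × 57/56. The effective effect is 0.5/√V on 57 degrees of freedom, and the equivalent unadjusted sample size is 30/V per group. For example, at r=0.3, V = 0.91 × 1.018 = 0.926, the effective effect is 0.520 and the equivalent n is 32.4.

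| r | V | Power, one-sided | Power, two-sided | Equivalent n per group |
|---|---|---|---|---|
| no covariate | 1 | 60.6% | 47.8% | 30 |
| 0 | 1.018 | 59.9% | 47.1% | 29.5 |
| 0.2 | 0.977 | 61.4% | 48.6% | 30.7 |
| 0.3 | 0.926 | 63.4% | 50.7% | 32.4 |
| 0.4 | 0.855 | 66.4% | 53.9% | 35.1 |
| 0.5 | 0.763 | 70.7% | 58.7% | 39.3 |

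**Step 4: break-even.** V = 1 when r² = 1/57 = 0.0175, so r is about 0.13. The worst case, r=0, costs 60.6 − 59.9 = 0.7 points one-sided and 47.8 − 47.1 = 0.7 points two-sided.

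**Step 5: simulation check.** With 20,000 simulated trials per setting, fitted one-sided ANCOVA gave power of 59.5%, 61.6%, 63.9% and 70.9% at r=0, 0.2, 0.3 and 0.5, in line with the table. Under no treatment effect it rejected in 4.8% to 5.2% of trials, so the level is kept.

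**Step 6: why not a change score.** A change score has effective effect d/√(2(1 − r)), which is below d whenever r is below 0.5. At d=0.5, one-sided, power is about 45% at r=0.2, 49% at r=0.3 and 54% at r=0.4, and it only returns to 61% at r=0.5. ANCOVA estimates the slope from the data instead of fixing it at 1, which suits two ratings made under different smoking conditions.

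**The case against.** The strongest reply is that nothing here is wrong. ANOVA-based methods can include ANCOVA, so the plan does not commit to an unadjusted test. If it did, that test would be valid after randomisation. This stands in full. A reader might infer that the plan has chosen an inferior analysis, or that leaving out the covariate brings bias or a raised false-positive rate; the documents support neither.

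Second, the benefit depends on figures the documents do not contain. This also stands. The P2 rating follows abstinence from midnight plus two further hours, with no matching request at P1, so the correlation could be low and below about 0.13 the adjustment loses a little. What remains is the asymmetry: at d=0.5 the most that can be lost is about 0.7 points, while r=0.5 would gain about 10.

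Third, the covariate may not match the outcome. No withdrawal instrument is named for P1 or for the P2 laboratory rating, and the Consent Process section says that most of the questionnaires are unpublished. Session P1 also mentions randomisation before it lists the symptom ratings, so their order within the visit is not explicit. Both points bear on how the fix is worded but do not defeat it. ANCOVA needs a covariate that correlates with the outcome and is unaffected by treatment, not an identical scale, and the P1 rating comes before drug use in a double-blind comparison.

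Fourth, the one-tailed argument in the plan is made for time-to-lapse alone. That is correct, so the two-sided figures are shown beside the one-sided ones.

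**Conclusion.** The point holds as an optional improvement to a secondary outcome. The plan names no baseline covariate for laboratory withdrawal although a pre-drug rating is already collected, and ANCOVA on that rating would cost almost nothing.

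At r=0.2 to 0.3 the gain is about 1 to 3 points of power, worth 0.7 to 2.4 extra participants per group. At r=0.5 it is about 10 points one-sided and 11 two-sided. These sizes rest on an assumed d of 0.5, an assumed r, an assumed sidedness and no dropout. The low cost is well supported; the size of the benefit is not known.

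A reader might take the 61% or 48% as showing that the trial is underpowered for withdrawal. That does not follow: the plan makes no power claim for withdrawal, and the 0.5 is illustrative. Nor does the point touch the primary outcome, whose stated power reproduces at 92.2%.

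**What to change.** In Data Analysis & Statistical Considerations, add one sentence: the P2 laboratory withdrawal score will be compared between groups by ANCOVA with treatment group and the P1 withdrawal score as terms.

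The sentence should make clear that:
- the covariate is the P1 rating, taken before any study medication and preferably before allocation is made;
- the routine withdrawal questionnaire at P2 is not the covariate, because it is completed after two weeks of treatment;
- the outcome is the P2 laboratory score itself, not its change from P1;
- the same instrument is used at P1 and in the P2 laboratory session where possible;
- the test is one-sided or two-sided, whichever is intended for this outcome.

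The cost is this wording and one degree of freedom (58 to 57). No new visit, questionnaire or data item is needed.

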STUDY TITLE: Combination Nicotine Patch / Lorcaserin for Smoking Cessation

NCT ID: NCT02906644

DOCUMENT VERSION DATE: February 12, 2018

Combination Nicotine Patch / Lorcaserin for Smoking Cessation

PI: [name].

Co-PI: [name].

PURPOSE OF THE STUDY:

This study proposes to investigate the potential efficacy of a combination of two FDA-approved agents, nicotine patch and lorcaserin, for smoking cessation treatment. The nicotine patch which provides a sustained low dose of nicotine is a nicotine receptor agonist. Lorcaserin, a serotonin 5-HT2C agonist, is a drug that is FDA-approved for weight loss, and has also recently been shown to be efficacious in a Phase II trial for smoking cessation (Shanahan et al, 2015). Given that these drugs act through distinct mechanisms it is hoped that the combination will prove more efficacious than either drug alone.

The aims of this small-scale (N=60) clinical trial are as follows:

- 1) To compare the efficacy of the nicotine patch / lorcaserin combination treatment vs. the nicotine patch alone in terms of leading to a reduction in ad libitum smoking behavior, withdrawal symptoms and time-to-lapse in a simulated quit-smoking situation;
- 2) To assess the tolerability of the combination treatment in terms of side effect frequencies and adherence to taking the medications;
- 3) To obtain an estimate of the smoking abstinence rate 10 weeks after a target quit-smoking date in smokers receiving combination treatment. Because the dichotomous outcome of abstinence vs. smoking is relatively insensitive from a statistical standpoint, no attempt will be made in this study to directly compare abstinence rates with the nicotine patch / lorcaserin combination vs. the nicotine patch alone. Instead, all participants will ultimately receive the combination treatment when making a quit-smoking attempt, yielding a larger sample with which to estimate the abstinence rate using combination treatment. This estimate will be compared with historical data on abstinence rates in a similar population of smokers;

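### The early-marker correlation states no term for randomised arm, although the arms are on different treatments while the marker is measured; the likely bias is small and easily removed

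*Combined protocol and SAP*

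**What the plan says.** The marker analysis is one sentence in Data Analysis & Statistical Considerations: "Abstinence will also be correlated with the reduction in ad libitum smoking in the first 2 weeks", with the aim "to determine whether smoking reduction may be a useful early marker of therapeutic efficacy". No arm covariate, within-arm analysis or arm-by-marker interaction is mentioned there or elsewhere.

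The Design Overview fixes what each arm is taking at that time: "Participants will be randomized to receive nicotine patch + lorcaserin or nicotine patch + placebo for the first 2 weeks". It continues: "After the first 2 weeks, all participants will receive the same combination treatment for the remainder of the study". The list of treatment groups gives Group A "21mg nicotine patch + lorcaserin 10mg twice daily for the 14 week study period" and Group B "21mg nicotine patch + placebo for the first 2 weeks; 21mg nicotine patch + lorcaserin 10mg twice daily for the next 12 weeks".

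The same reduction is also a between-arm endpoint: "Secondary outcomes that will be compared between groups include the percent reduction in ad libitum smoking during the first 2 weeks". For abstinence, aim 3 in Purpose of the Study treats the two arms as one sample, because "all participants will ultimately receive the combination treatment when making a quit-smoking attempt, yielding a larger sample".

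**The concern.** The plan expects the marker to depend on arm, since it tests for that difference, and then relates the marker to abstinence without mentioning arm. If the arms are pooled, the coefficient has two parts. One is the association among smokers on the same treatment. The other is the arm difference in reduction multiplied by any arm difference in abstinence. Only the first shows whether a smoker who cuts down more on a given treatment is more likely to quit.

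There is also a problem of interpretation. In Group A the marker is an early response to the treatment on which the participant later tries to quit. In Group B it is a response to the patch alone, while the quit attempt is made on the combination. One coefficient cannot show under which treatment the marker works. That matters somewhat, because the study is meant as pilot work for a larger trial of the combination, each agent alone and placebo.

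**Working it through.** **The plan's own figure.** No figure is given for the marker correlation. The only power statement (over 90%) is for time-to-lapse: 30 per group, effect about 0.8 SD, one-sided 5%. It reproduces at 92.2% with the noncentral t, but has no bearing on the marker.

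**Inputs.**
- From the documents: 30 per group, 60 in all; arms on different treatments in weeks 1-2 and on the same treatment afterwards; 14 against 12 weeks of lorcaserin.
- Assumed, because the documents give none: arm difference in reduction, d = 0.3 to 0.8 within-arm SDs; mean abstinence p of 22% or 30%; arm difference in abstinence, dp; within-arm correlation, rho.

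**Formula.** With equal arms and V the mean within-arm variance of abstinence,

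pooled r = [rho × sqrt(V) + d × dp / 4] / sqrt[(1 + d²/4) × p(1 − p)].

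**Case 1: equal abstinence (dp = 0).** The formula reduces to rho / sqrt(1 + d²/4).
- d = 0.3: 1/sqrt(1.0225) = 0.989, a loss of about 1%.
- d = 0.5: 1/sqrt(1.0625) = 0.970, about 3%.
- d = 0.8: 1/sqrt(1.16) = 0.928, about 7%; rho = 0.30 becomes 0.28.

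For scale, the standard error of r on the Fisher z scale at N = 60 is 1/sqrt(57) = 0.13. Simulation at d = 0.8 with a within-arm r of about 0.31 gives power of about 63% pooled and 69% adjusted. The false-positive rate stays at about 5%, so here pooling only dilutes.

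**Case 2: no within-arm association (rho = 0), abstinence differs.** At p = 0.22, an odds ratio of 3 is about 31% against 13%, so dp = 0.18. With d = 0.8, pooled r = (0.8 × 0.18 / 4) / sqrt(1.16 × 0.22 × 0.78) = 0.036 / 0.446 = 0.08. False-positive rates of the pooled test (simulated, 30 per arm, 22% abstinent, two-sided 5%):

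| Abstinence odds ratio, A vs B | d = 0.5 | d = 0.8 |
|---|---|---|
| 1.25 | 5.2% | 5.3% |
| 1.5 | 5.3% | 5.4% |
| 2 | 5.5% | 6.7% |
| 3 | not tabulated | 9.4% |

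A separate simulation at 30% mean abstinence and d = 0.8 gives 4.9%, 6.2% and 9.7% for abstinence differences of 0, 10 and 20 points. The arm-adjusted correlation stays at 5.0-5.1% in those same cases.

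**How plausible is an odds ratio of 3?** Background & Significance reports continuous abstinence of 15.3% on lorcaserin twice daily and 5.6% on placebo. The odds ratio is (0.153/0.847) / (0.056/0.944) = 0.1806 / 0.0593, about 3.05. That is drug against no drug. Here both arms take the combination from week 3, including the two weeks before the quit date, and differ by 14 − 12 = 2 weeks. An odds ratio of 3 would give those two weeks the whole drug effect.

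**Case 3: the association differs by arm.** If r were 0.4 in Group A and 0 in Group B, with equal abstinence, pooled r would be 0.20 at d = 0 and 0.20 × 0.928 = 0.19 at d = 0.8. That describes neither arm.

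**The case against.** The sentence neither specifies nor excludes an arm-adjusted or within-arm correlation, so pooling is inferred. That is so. It remains the natural reading, given that abstinence is treated as one sample, and if something else is meant the text should say it.

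The stated aim is an early marker of efficacy; the plan does not say that prediction within a treatment arm is the target. This also stands, but a marker that merely stands in for randomised arm would add nothing to knowing the arm.

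The strongest objection is size. Dilution of 1-7% is well inside the sampling error of r with 60 participants, and a false positive needs arm to affect abstinence as well as reduction. Two extra weeks of lorcaserin are unlikely to do that strongly. This stands and limits the point. A reader might infer false-positive rates of 9-15%, or that the next trial's choice of marker would be misled. The documents do not support either. About 9% needs odds ratio 3 together with d = 0.8, and the 0.8 is quoted for time-to-lapse, not for smoking reduction. About 15% needs a still larger arm difference, such as d = 1.2 with odds ratio 3 or a 30-point abstinence gap at d = 0.8; neither has a basis in the documents.

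Finally, adjustment brings little power. In simulation with a within-arm r of about 0.33, pooled correlation against logistic regression with arm gave 72% against 70% at d = 0.3, 71% against 70% at d = 0.5, and 67% against 72% at d = 0.8. The case for adjustment is therefore that the coefficient can be interpreted, and power is a minor consideration.

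**Conclusion.** The point holds as a minor one. As written, the marker analysis does not account for arm, although the design makes treatment differ during the marker window and the plan tests for that difference. The coefficient would mix between-arm and within-arm components, and its meaning differs between Groups A and B. The numerical bias is probably small: a 1-7% loss in r if abstinence is equal, and a false-positive rate of about 5-7% for odds ratios of 1.5 to 2. All of these sizes rest on assumed arm effects, abstinence rates and within-arm correlations. The analysis is exploratory. The time-to-lapse comparison, the tolerability summaries and the overall abstinence estimate do not depend on it.

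**What to change.** State in the plan that the marker analysis includes randomised arm. Either an arm-adjusted partial correlation or a logistic regression of weeks 7-10 abstinence on percent reduction plus arm will serve. Choose one before unblinding, so that the choice between pooled and adjusted results is not made after seeing them. Report the association within each arm beside it, labelled descriptive; any arm-by-marker interaction should carry the same label. Arm adjustment assumes a common association, and only the within-arm estimates show whether a response to patch alone and a response to the combination carry the same information.

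The cost is one degree of freedom and no extra data, visits or participants. The within-arm estimates will be imprecise, and the report should say so. With 30 participants, 80% power (two-sided 5%) is reached only at r of about 0.49, against about 0.35 with all 60. At an assumed 22% abstinence there are about 0.22 × 60 = 13 abstainers in total, or 6-7 per arm.
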